2.4. Predicting Cognitive Trajectories

We have applied the AD Progression Classifier to 72 NL (40 with amyloid data available), 173 MCI (87 with amyloid data available), and 50 AD subjects from the ADNI database, comparing the classifier score as a predictor of decline in MMSE, CDR-sum of boxes (CDR-sb), and ADAS-Cog 11 to other predictors (baseline MMSE, baseline CDR-sb, baseline ADAS-Cog 11, and amyloid cortical average Standardized Uptake Value Ratio (SUVR)). Results indicated that the AD Progression score was a significant predictor of decline in these measures and a better predictor than the other variables tested⁶. The classifier was also applied to patients in a trial of bapineuzumab, with the result that more severe hypometabolism at baseline as identified by ADMdx’s AD Progression Classifier was a strong predictor of subsequent clinical decline over the course of the trials (18).

2.5 Glucose Metabolism as a Measure of Drug Effects

[figure not shown]

Figure 4. Increases (red) and decreases (blue) in glucose metabolism relative to placebo at a lower and higher dose of an NK1 antagonist. Eigenplot at right shows individual subject expression of the primary pattern of change relative to placebo, and relative to one another, for each treatment dose.

In addition to measuring disease-related changes in neuronal activity, FDG PET can capture drug-related effects, even in small group sizes and at acute doses, depending upon effect. Figure 4 shows the acute effects of a lower and higher dose of an NK1 antagonist compound as measured in a double-blinded randomized crossover study of 10 normal healthy volunteers. Acute changes observed in glucose metabolism were consistent with clinical effects observed in a separate chronic dosing study. The graph in Figure 4 shows each subject's expression of the primary pattern of change for placebo and each treatment dose. These results were obtained using ADMdx's multivariate pattern analysis software (NPAIRS), which uses Principal Component Analysis (PCA) and Canonical Variate Analysis (CVA) to segregate signal from noise, identify the component patterns contributing to overall effect, determine the relative contribution of each pattern, measure each subject's relative expression of the pattern, and provide metrics regarding the reproducibility and predictive power of the group results, and identify patterns of effect. It provides a powerful tool to gain insight into treatment effects (21, 22).

2.6 Tau Imaging as a Measure of Drug Effect

Several kinases (e.g., MAPK PCK) are deregulated in AD and they contribute to tau hyperphosphorylation and the formation of neurofibrillary tangles (31, 32). These observations link rasagiline to tau hyperphosphorylation, neurofibrillary tangle formation, and possibly detectable effects on tau imaging (33, 34)

The incorporation of Tau imaging with the novel ligand ¹⁸F-AV-1451 (Avid Radiopharmaceuticals) provides the opportunity to advance understanding of neuroprotection, neurofibrillary tangles, and tau imaging. This is the first clinical trial in which tau imaging will be required at baseline. Tau imaging will be secondary outcome of the trial, and there will be opportunities to understand the information provided by tau imaging as a complement to FDG imaging.

3. STUDY OBJECTIVES and ENDPOINTS

3.1 Primary Objective

To determine if exposure to 1 mg of rasagiline once daily is associated with improved regional brain metabolism in the treatment group compared to the placebo group after a 24-week double blind study treatment in Patients with Mild to Moderate Alzheimer's Disease

3.2 Secondary Objectives

- To evaluate the efficacy of rasagiline 1 mg once daily compared to placebo after a 24-week treatment on cognition (ADAS-Cog 11), activities of daily living (ADCS-ADL), global function (CGIC), and neuropsychiatric symptoms (NPI)
- To evaluate the efficacy of rasagiline 1 mg once daily compared to placebo after a 24-week treatment on measures of executive function (Digit Span test, and Controlled Oral Word Association Test [COWAT] for verbal fluency)
- To evaluate the safety and tolerability of rasagiline as measured by incidence of adverse events/serious adverse events (AEs/SAEs) clinical laboratory test data, vital signs, 12-lead EKG data,
- To evaluate the correlation of FDG-PET results to ¹⁸F-AV-1451 (T807) Tau PET results
- To correlate the relationship of ¹⁸F-AV-1451 (T807) Tau imaging to clinical measures

3.3 Primary Endpoint

The primary study endpoint is the change from screening visit (baseline FDG) to Week 24 in regional glucose metabolism as measured by standardized uptake value ratio (SUV_r) obtained through the FDG-PET.

3.4 Secondary Endpoints

- Change from Baseline ¹⁸F-AV-1451 Tau PET imaging SUV_r results to Week 24 results
- Change from Baseline to Week 24 on the scores of MMSE, ADAS-Cog 11, CGIC
- Change from Baseline to Week 24 on the scores of NPI and ADCS-ADL
- Change from Baseline to Week 24 on the scores of Digit Span test, COWAT and QoL-AD/Study Partner
- Safety and tolerability as measured by incidence of adverse events/serious adverse events (AEs/SAEs) clinical lab test data, vital signs, 12-lead EKG data
- Proportion of subjects with adverse events, serious adverse events and adverse events leading to discontinuation over the 24-week double blind treatment period
- Proportion of subjects with laboratory abnormalities
- Proportion of subjects with ECG abnormalities

[figure not shown]
4. STUDY DESIGN

This is a 24 week, Phase II, randomized, double blind, placebo controlled, parallel group, proof-of-concept three-site study, to evaluate the effect of rasagiline in the regional brain metabolism on FDG PET in patients with mild to moderate Alzheimer's disease.

The study consists of two phases: a 24-week double blind placebo controlled treatment period with a 4-week follow-up period. Patients will be randomized to a 1:1 ratio at Baseline to receive rasagiline or matching placebo treatment.

The study drug will be given as 0.5 mg dose once daily for the first 4 weeks then increased to 1 mg dose daily tablet for the next 20 weeks. A total of 50 subjects will be enrolled and will be randomized to a 1:1 ratio. Twenty-five participants will receive rasagiline and the other 25 will receive matching placebo for the 24-week treatment period.

Figure 5. **Research Schematic**

Visit 1 – Screening visit (within a 60-day period); MRI, FDG PET and ¹⁸F-AV-1451 Tau imaging

Visit 2 – Baseline (Week 1)

Visit 3 Week 4; increase dose from 0.5 mg QD to 1 mg QD

Visit 4 Week 8

Visit 5 –Week 24; blood draws, FDG PET & ¹⁸F-AV-1451 Tau imaging, end of treatment

Visit 6 – Follow-up Visit/ Week 28; end of study/early discontinuation

5. SUBJECT SELECTION AND WITHDRAWAL

5.1 Inclusion Criteria

1. Males or females 50 to 90 years of age inclusive
2. Diagnosis of probable AD according to National Institute of Neurological and Communicative Disorders and Stroke-Alzheimer's Disease and Related Disorders Association (NINCDS-ADRDA) criteria
3. Positive fluorodeoxyglucose PET ([¹⁸F]-FDG PET) scan compatible with AD as determined by the ADM Diagnostics LLC (ADMdx) criteria
4. Must be willing to undergo ¹⁸F-AV-1451 Tau imaging at Screening and Week 24 visits
5. Mini-Mental State Examination (MMSE) score between 12-26 inclusive
6. Must have a study partner who is able and willing to comply with all required study procedures
7. Have at least eight years of education and should have previously (in pre-AD condition) been capable of reading, writing, and communicating effectively with others in English
8. If receiving therapy with a cholinesterase inhibitor and/or memantine, the dose of these agents has been stable for at least 60 days prior to screening
9. Willing and able to provide informed consent by either the subject or subject's legal representative
10. Willing and able to comply with study visits, treatment plan, laboratory tests, brain imaging and other procedures
11. Females must be postmenopausal

5.2 Exclusion Criteria

1. Any clinically relevant neurological disorder capable of producing a dementia syndrome including Parkinson's disease, stroke, vascular dementia, dementia with Lewy bodies, frontotemporal dementia and others
2. Psychosis or is receiving antipsychotic treatment
3. MRI findings indication of a non-Alzheimer's disease diagnosis
4. History of melanoma; history of malignancy within the past five years with the exception of basal cell or squamous cell cancer, in-situ cervical cancer, or localized prostate cancer
5. History of Deep Brain Stimulation (DBS)
6. History of seizure in the past three years prior to randomization
7. Any contraindication of having brain MRI
8. Any contraindication of having PET (inability to lie flat and still for the duration of the scan, intolerance to previous PET such as hypersensitivity reaction to PET ligand or imaging agent)
9. The subject has any unstable medical illness including hypertension, congestive heart failure, chronic obstructive pulmonary disease, renal failure, liver failure or other organ compromise

10. Uncontrolled hypertension (systolic blood pressure [BP] \geq 160 mmHg, or diastolic BP \geq 100 mmHg; US National Institutes of Health [NIH] Seventh Report of the Joint National Committee [JNC 7] criteria). Hypertensive patients whose BP is controlled with medication to systolic BP $<$ 160 mmHg and diastolic BP $<$ 100 mmHg are eligible.
11. Baseline laboratory studies that are 1.5 times above or below the highest and lowest range of normal values
12. Other clinically important abnormality on vital signs, physical examination, neurological examination or laboratory results, that could compromise the study or be detrimental to the subject
13. Have either: 1) Screening ECG with QTc $>$ 450 msec if male or QTc $>$ 470 msec if female; or 2) A history of additional risk factors for Torsades de Pointes (TdP) (e.g., hypokalemia, family history of Long QT Syndrome) or are taking drugs that are known to cause QT-prolongation; Patients with a prolonged QTc interval in the setting of intraventricular conduction block (e.g. right bundle branch block [RBBB] or left bundle branch block [LBBB], may be enrolled with sponsor approval; or 3) History of atrial fibrillation
14. The patient has taken rasagiline or any other MAOIs within 90 days prior to the Screening/Baseline Visit
15. The subject has an allergy to rasagiline
16. Other disallowed medications (taken within 30 days before the Screening/Baseline Visit and during the study) include anticholinergics, meperidine, dextromethorphan, tramadol, St. John's wort, methadone, cocaine, ciprofloxacin, or other CYP1A2 inhibitors
17. Has had a PET scan or radiotherapy within 6 months prior to the Screening visit
18. Has participated in an investigational drug or device study within 30 days prior to Screening
19. Unable to swallow uncrushed oral medication in tablet form
20. Has any condition or reason that, in the opinion of the investigator, could interfere with the ability of the patient to participate or complete the trial, or places the patient at undue risk or complicates the interpretation of safety or efficacy data

5.3 Subject Recruitment

Subjects will be recruited from three sites of the Cleveland Clinic, Lou Ruvo Center for Brain Health -- Las Vegas, Cleveland Main Campus and Lakewood site. Subjects may be referred directly to the clinical trial from community physicians. Advertising materials used for the trial will be approved by the Cleveland Clinic Institutional Review Board (IRB) prior to implementation.

5.4 Subject Withdrawal

Patients and caregivers are informed that they have the right to withdraw from the study at any time without prejudice or loss of benefit to which they are otherwise entitled.

The investigator or sponsor may withdraw a patient from the study in the event of an inter-current illness, adverse event, non-compliance, protocol violation and other reasons concerning the health or wellbeing of the patient.

Following are specific circumstances justifying withdrawal:

- Development of an inter-current medical condition or need for concomitant treatment that precludes further participation in the trial
- Unacceptable toxicity or any adverse event that precludes further participation in the trial
- The investigator removes the patient from the trial in the best interests of the patient
- Non-adherence to study regimen as determined by pill count
- Patient withdraws consent to continued participation in the trial

Patients who withdraw prior to study completion will be asked to return to the clinic to complete visit 6 (end of study) assessments.

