DIETARY ADJUSTMENT	
High tyramine-containing foods will be avoided:
 
 • Sausages, salami, pickled herring • Fava beans • Tap beers, non-pasteurized beers • Sauerkraut, yeast extract, soybean products including soy sauce • Aged cheeses
DRUG DOSAGE AND FORMULATION	
Subjects will take one 0.5 mg dosage Rasagiline tablet or the matching placebo once a day orally from Baseline visit to Week 4 visit. The dose will be titrated to one 1 mg dosage tablet or the matching placebo once a day starting on Week 5 through Week 24.

DURATION OF PARTICIPATION	
This is a 34-week study comprised of 7 in-clinic visits

PLACEBO	
A matching oral placebo will be used

ROUTE OF ADMINISTRATION	
Oral

PROCEDURES	
Physical and neurological exam, MRI, [18F]-FDG PET, ¹⁸F-AV-1451 Tau PET, ECG, vitals, clinical laboratory tests, MMSE, ADAS-Cog 11, CGIC, NPI, ADCS-ADL, Digit Span, COWAT, QoL-AD/Study Partner

STATISTICAL CONSIDERATION	
Intent-to-Treat (ITT) - The primary FDG analysis will include all patients who received both a screening and end of study scan of acceptable quality.
 
Modified Intent-to-Treat (mITT) – All randomized subjects who have been dispensed study medication and have one post-baseline visit during the blinded phase of the study.
 
Per-protocol (PP) population – All ITT subjects who complete the study (Week 24) and have ingested between 80% to 120% of the prescribed study medication as measured by pill count.
 
Observed case – An observed case analysis of all patients completing the study will be conducted.
 
Last Observation Carried Forward (LOCF) – Clinical data imputation will use the LOCF approach for missing patients.
 
Responder analysis – Responders will be defined as those that have a significant improvement on brain metabolism on FDG for the whole brain or for any of the pre-specified regions.
 
A secondary analysis will compare the changes in FDG at 24 weeks compared to the projected expected metabolism based on the Baseline FDG findings.

ADVERSE EVENTS	
SAFETY
 
Orthostatic vital signs, ECG, hematology, chemistry, TSH, B12 and urinalysis (UA) collected at Screening and at end of study

	
TOLERABILITY
 
Side effects data will be collected and converted to systems data using a data dictionary.
 
DSMB No Independent DSMB is required.

--	--

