7.6 Visit 6 – Follow-up Visit/End of Study/Early Discontinuation (Week 28)

This visit will occur at the end of Week 28 with a visit window of +/- 5 days. This will be a follow-up visit after the treatment phase.

The following activities will be completed:

- Record orthostatic vital signs and body weight
- Perform the following assessments:
 - ADAS-Cog 11
 - CGIC
 - NPI
 - ADCS-ADL
 - Digit Span
 - COWAT

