9.1 Safety Assessments

At each study visit, adverse events (AEs) and serious adverse events (SAEs) will be reviewed; vital signs and weight will be done for safety assessments. Hematology, blood chemistry, and liver function tests will be collected at Screening visit and Week 24.

Potential adverse events will be reviewed by the Principal Investigator and documented. Adverse events include signs or symptoms that may or may not be related to study medication, abnormalities detected on physical examination, or clinically significant laboratory abnormalities. Adverse events will be graded (mild: causing no limitation of usual activities; moderate: causing some limitation of usual activities; severe: causing inability to carry out usual activities) and recorded on case report forms.

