9.7 Clinical Laboratory Evaluation

Hematology, chemistry, liver function, B12, TSH levels and urinalysis will be collected at Screening and Week 24 visits. Laboratory samples to be tested consist of the following:

Hematology	Chemistry	Liver Function	Other Tests
Hemoglobin	Na	Albumin	TSH
Hematocrit	K	Total bilirubin	B12
RBC	Cl	Direct bilirubin	Urinalysis
Indices	CO2	Alkaline	
WBC	Glu	phosphatase	
Platelet count	BUN	Total Protein	
Differential count	Cr	AST - Aspartate	
	Ca	Transaminase	
		ALT -- Alanine	
		Transaminase	

Laboratory reports will be reviewed, signed and dated by the principal investigator. If any laboratory abnormalities have emerged in the course of the 24-week clinical trial, laboratory measures of that test will be repeated. The investigator will determine if abnormal values are clinically significant or not. If abnormalities persist, patients will be referred to their primary care physicians for treatment of the abnormality.

Quest Diagnostics and the Cleveland Clinic Laboratory will function as the research reference laboratories and will conduct all laboratory assessments.

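### Early withdrawals are sent to Visit 6, which has no laboratory tests, ECG, MMSE or QoL-AD, so they have no scheduled post-baseline value for four named secondary endpoints

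*Protocol*

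**What the plan says.** Section 5.4 of the protocol directs early withdrawals to one visit: "Patients who withdraw prior to study completion will be asked to return to the clinic to complete visit 6 (end of study) assessments". Among the reasons for withdrawal it lists "Unacceptable toxicity or any adverse event that precludes further participation in the trial". Section 5.5 adds that withdrawals are not replaced.

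Visit 6 has two roles, Week 28 follow-up and early discontinuation, but section 7.6 describes only the former: "This will be a follow-up visit after the treatment phase". Its list covers orthostatic vital signs, weight, ADAS-Cog 11, CGIC, NPI, ADCS-ADL, Digit Span and COWAT. The Visit 6 column of Table 2 adds adverse-event recording and drug accountability.

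On laboratory timing, section 9.1 says: "Hematology, blood chemistry, and liver function tests will be collected at Screening visit and Week 24". Section 9.7 agrees: "Hematology, chemistry, liver function, B12, TSH levels and urinalysis will be collected at Screening and Week 24 visits". Section 9.5 places the ECG at screening and Week 24. Section 8.1.1 places the MMSE at Screening, Baseline and Week 24, and section 8.2.6 places the QoL-AD at Baseline and Week 24.

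Section 3.4 names as secondary endpoints "Proportion of subjects with laboratory abnormalities", the matching proportion for ECG, and the change to Week 24 in MMSE and in QoL-AD.

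**The concern.** The visit that receives withdrawals was built as an off-drug follow-up for patients who have already had their Week 24 assessments. For those patients, leaving out the laboratory panel, ECG, MMSE and QoL-AD costs nothing. For a patient who stops at, say, Week 10, Visit 6 is the last planned contact, and none of the four will be measured.

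Toxicity is a listed reason for withdrawal, so the missing safety values may be related to what they would have shown. With 25 patients per arm, a handful of untested patients can change an abnormality proportion visibly. A laboratory value or ECG not taken at withdrawal cannot be recovered later by any analysis.

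**Working it through.** The plan states no figure for this point, so the check is a comparison of schedules followed by an illustration on stated assumptions.

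**Step 1: what is measured, and when (section 7, Table 2, Appendix B)**

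| Measure | Before dosing | Week 4 | Week 8 | Week 24 (Visit 5) | Visit 6 |
|---|---|---|---|---|---|
| Laboratory panel | Screening | no | no | yes | no |
| ECG | Screening | no | no | yes | no |
| MMSE | Screening, Baseline | no | no | yes | no |
| QoL-AD | Baseline | no | no | yes | no |
| ADAS-Cog 11, NPI, ADCS-ADL, Digit Span, COWAT | Baseline | yes | yes | yes | yes |
| CGIC | Baseline | yes | no | yes | yes |

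For a patient who leaves before Week 24 and attends Visit 6, the number of scheduled post-baseline values is 0 for each of the first four rows. The remaining clinical scales are collected at withdrawal. The visit text, both schedule tables and the procedure sections agree on this.

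**Step 2: how many patients.** Planned enrolment is 50 (section 4). The documents give no dropout rate, so the rates here are assumptions: 10% gives 0.10 × 50 = 5 patients, 20% gives 10 and 30% gives 15.

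**Step 3: possible effect on an abnormality proportion.** Assume 5 of the 25 patients in an arm truly develop an abnormality (5/25 = 20%), and that k of these five withdraw and are never tested. The observed proportion is (5 − k)/25 if all randomised patients are counted, or (5 − k)/(25 − k) if only tested patients are counted.

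| k | All randomised | Tested only |
|---|---|---|
| 0 | 5/25 = 20% | 5/25 = 20% |
| 1 | 4/25 = 16% | 4/24 = 16.7% |
| 2 | 3/25 = 12% | 3/23 = 13.0% |
| 3 | 2/25 = 8% | 2/22 = 9.1% |
| 4 | 1/25 = 4% | 1/21 = 4.8% |
| 5 | 0/25 = 0% | 0/20 = 0% |

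Both denominators are shown because the SAP does not choose between them. Its section 5 assigns safety to the ITT population, but its section 11 describes no laboratory or ECG analysis.

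**Step 4: between arms.** Suppose both arms have a true 5/25 and count all randomised patients. With k = 3 in both arms, each reads 8% and the difference stays at 0. With k = 3 in one arm only, that arm reads 8% against 20%, a false difference of 12 percentage points in its favour. The direction therefore depends on which arm loses untested patients.

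**Step 5: MMSE and QoL-AD.** SAP section 9 fits a linear mixed model to all randomised participants. A patient with pre-treatment scores only stays in the model but supplies no observed change. If the LOCF rule of protocol section 11.2 were applied instead, the only score available to carry forward would be a pre-treatment one.

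**The case against.** The strongest reply is that these patients are not lost to the safety evaluation. Section 7.7 provides unscheduled visits for unusual side effects. Section 9.1 counts clinically significant laboratory abnormalities as adverse events, and section 9.7 requires repeat tests when an abnormality has emerged. Section 12.2 calls for examination where appropriate, recording of abnormal diagnostic results, and follow-up of each event. Visit 6 itself keeps orthostatic vital signs, adverse-event recording and six clinical scales, and adverse events leading to discontinuation are a separate endpoint. Patients who stop for toxicity are arguably the most likely to be tested ad hoc. All of this stands, but none of these provisions schedules a laboratory test, ECG, MMSE or QoL-AD at withdrawal.

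A reader might also infer several stronger things that the documents do not support:

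- **Withdrawals contribute nothing to these endpoints.** Ad hoc results may exist, and pre-treatment MMSE and QoL-AD scores enter the mixed model.
- **The proportions are computed on completers only.** No passage says so; the denominator is unspecified.
- **The drug will look safer than it is.** The gap applies equally to placebo, and step 4 shows that the direction depends on withdrawal by arm.
- **Scores from an early Visit 6 will be filed at Week 28 and dropped from a 24-week analysis.** No such rule is written. SAP section 9 treats time as continuous, which accommodates the actual day; the SAP is merely silent on placement.
- **The Synopsis contradicts the schedule.** It has "chemistry, TSH, B12 and urinalysis (UA) collected at Screening and at end of study", and Visit 6 carries the end-of-study label. But section 6.5 equates end of study with Week 24, and the Synopsis uses the same term for the closing FDG scan, which is done only at Week 24. What remains is one label used for two visits.

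**Conclusion.** The gap is certain, because it is read directly from the schedule: a fully compliant early withdrawal has no scheduled post-baseline laboratory test, ECG, MMSE or QoL-AD, and all four feed named secondary endpoints. How many patients this affects is unknown; 5 to 10 of 50 rests on an assumed 10% to 20% withdrawal rate.

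Under-counting of laboratory and ECG abnormalities is possible but not shown. It requires that abnormalities be associated with withdrawal and that the affected patients are not tested ad hoc. The fall from 20% to 8% or 9% illustrates the size under those assumptions and is not a forecast. No direction can be stated for the comparison between arms. The point concerns secondary and safety endpoints, and it is worth correcting because the remedy is cheap and the missing data cannot be obtained afterwards.

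**What to change.** 1. In protocol section 7.6, Table 2 and Appendix B, separate Early Discontinuation from the Week 28 follow-up. Leave the Week 28 content unchanged. Give Early Discontinuation the current Visit 6 content plus the Visit 5 laboratory panel, ECG, MMSE and QoL-AD.
2. Include these results in the laboratory and ECG abnormality endpoints. In SAP section 11, state how untested patients are counted and report the number tested in each arm.
3. In SAP section 9, state that early-discontinuation scores enter the models at the actual time since randomisation. This clarifies the plan and is consistent with its continuous time variable.
4. Clarify the end-of-study label, which section 6.5 uses for Week 24 and sections 5.4 and 7.6 use for Visit 6.

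The cost is one protocol amendment and short SAP additions. For each patient who withdraws, it means one blood draw with the rest of the existing panel, one ECG and two short scales, at a visit the patient is already asked to attend. All are procedures already used at Visit 5, and no new staff are needed.
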